6.2.2 Caregiver Global Impression–Improvement (CaGI-I)

The question of the CaGI-I is identical to the question utilized in the Rett Natural History Study regarding Overall Function and Well-Being and asks "How would you describe your child's overall function?" The CaGI-I will be administered at Visits 6, 7, 8, 9, and 10. Completion of this scale requires the caregiver to rate how much the subject's illness has improved or worsened relative to a baseline state. A 5-point scale is used with the following response options: much improved, improved, unchanged, worse, and much worse. The data will be presented both by text response and also by numeric value in which 1= much improved, 2= improved, 3=unchanged, 4=worse, 5=much worse.

In this study, the illness being assessed is RTT as a whole.

6.2.3 Overall Quality of Life Rating of the Impact of Childhood Neurologic Disability (ICND) Scale

The Impact of Childhood Neurologic Disability (ICND) Scale was developed to evaluate the impact that a child's condition has on the child's and the family's everyday life at the present time and during the previous 3 months (Camfield et al. 2003).

In this study, the caregiver will complete only the Overall Quality of Life rating of the ICND. The caregiver rates overall quality of life of the subject by responding to the following: "Please rate your child's overall 'Quality of Life' on the scale below. Choose the number which you feel is best and circle it". The choices range from 1 ("Poor") to 6 ("Excellent").

The assessment will be administered at Baseline, Visits 6, 7, 8, 9, and 10.

Final Version: 1.0

6.3 Safety Assessments

6.3.1 Physical Examination

A general physical examination will be conducted at Screening, Baseline, and Visits 3, 4, 5, 6, 7, 8, 9, and 10. When a study visit takes place off-site, the physical examination will not be required. The physical exam procedures will include the following organ systems:

- Neurological
- Head, ears, eyes, nose, and throat
- Skin
- Cardiovascular
- Respiratory
- Abdomen
- Genitourinary (optional)
- Musculoskeletal

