Abbreviations: AE=adverse event; EOT=end of treatment; *MECP2*=methyl-CpG-binding protein 2 gene; N/A=not applicable; PK=pharmacokinetic; RTT=Rett syndrome; SAE=serious adverse event; T3=triiodothyronine; T4=thyroxine; TSH=thyroid stimulating hormone

- The first dose of study drug will be administered after all Baseline assessments are completed, or, if the Investigator judges that it is too late in the day, on the following day. In that case, the second day is still considered part of the Baseline visit. The day the first dose is taken will be considered Day 1.
- Timing of post-Baseline visits will be calculated from the first day of dosing (Day 1) (i.e., the Week 2 visit will occur 2 weeks [14±3 days] after the first day of dosing).
- The Baseline and Week 12 visits must be done at the clinic. All other study visits may be done in the clinic or off-site. Study visits may be done off-site at the discretion of the Principal Investigator and only with the prior approval of the Sponsor or Medical Monitor. When a study visit takes place off-site, the physical examination will not be required. Weight should be measured whenever possible at off-site visits.
- d If documentation of the mutation is not adequate, genomic testing for a mutation in the MECP2 gene may be conducted as part of Screening.
- e Vital signs will include body temperature, resting respiration rate, sitting systolic and diastolic blood pressure, and pulse rate. The sitting blood pressure should be measured after the subject has been sitting or supine for ≥3 minutes.
- f ECGs will be completed in triplicate at Visit 1 (Screening), at Visit 2 (Baseline), both predose and at 2 hours (±15 minutes) after dosing, and at Visit 6 (Week 12). A single ECG will be completed at all other designated visits.
- A predose PK blood sample must be collected before administration of study drug at Baseline (Visit 2). After the first dose of study drug is administered, two PK samples will be collected: the first, 2 hours (±15 minutes) after dosing, as close as possible to the postdose ECG, and the second, at least 1 hour after the first.

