Abbreviations: AE=adverse event; EOT=end of treatment; ET=early termination; SAE=serious adverse event

Study visits may be done in the clinic or off-site. Study visits may be done off-site at the discretion of the Principal Investigator and only with the prior approval of the Sponsor or Medical Monitor. The EOT visit should be done in the clinic whenever possible. When a study visit takes place off-site, the physical examination will not be required. Weight should be measured whenever possible at off-site visits.

b Vital signs will include body temperature, resting respiration rate, sitting systolic and diastolic blood pressure, and pulse rate. The sitting blood pressure should be measured after the subject has been sitting or supine for ≥3 minutes.

Pharmacokinetic samples will not be collected at the Week 104 visit or at an ET visit during Treatment Period B. Pharmacokinetic samples will be collected, if possible, at the visit immediately following any SAE or following any AE leading to discontinuation.

- d At the Week 104 EOT/ET visit, the caregiver diary will be returned and reviewed, but no diary will be dispensed.
- ^e Caregiver interviews will be conducted remotely via telephone during Treatment Period B, at or before the final study visit (Week 104 [EOT/ET]). Participation in the caregiver interview is an optional component of the study requiring a separate informed consent.
- f Study drug will be dispensed at the site during the Baseline visit when the visit is conducted in the clinic. For the remainder of the study, investigational product will be shipped directly to the subject. Study drug shipment, return, and accountability will be performed in accordance with the drug distribution plan.
- A 30(+4)-day safety follow-up telephone or telemedicine contact is to be completed for subjects who complete the treatment period of the study or discontinue prematurely from the study (and do not begin to take marketed trofinetide within the 30 days after completing the treatment period of the study).

TABLE OF CONTENTS

SPONS	SOR SIGNATURE PAGE	2
DECLA	ARATION OF INVESTIGATOR	4
PROTO	OCOL SYNOPSIS	5
TABLE	OF CONTENTS	20
LIST O	F TABLES	25
	F FIGURES	
	F ABBREVIATIONS AND DEFINITION OF TERMS	
1	INTRODUCTION	
1.1	Background Information	
1.2	Investigational Product	
1.3	Previous Clinical Experience	
1.3.1	Clinical Pharmacology	
1.3.1.1	Linearity and Dose Proportionality	
	Comparison of Single-Dose and Multiple-Dose Pharmacokinetics	
	Absorption	

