2.1.1 Primary Endpoints

The safety endpoints are as follows:

- treatment-emergent adverse events (TEAEs)
- serious adverse events (SAEs)
- withdrawals due to adverse events (AEs)
- potentially clinically important changes in other safety assessments

The pharmacokinetic (PK) endpoints are as follows:

- whole blood concentration of trofinetide
- trofinetide PK parameters using the population PK approach

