- Observed: ≤450, 451 - ≤480, 481 - ≤500, and >500; >450; >480.
- Change from Baseline: ≤10, 11 – 30, 31 – 60, and >60; >30.

For cardiologist's interpretations, the number and percentage of subjects with ECG results that are determined as normal or abnormal will be summarized at scheduled visits. The overall post-baseline worst interpretation will also be summarized (i.e. if a subject has one or more post-baseline ECG results that is/are considered as abnormal, this subject will be counted in the abnormal category). Cardiologist's interpretations will also be summarized in a shift table. The shifts from Baseline to overall post-Baseline worst interpretation will also be presented. For the by-visit shift summary, the denominator is the number of subjects with non-missing cardiologist's interpretation at Baseline and the given visit. For the summaries of shift from Baseline to the overall post-Baseline worst interpretation, the denominator is the number of subjects with non-missing Baseline and at least 1 post-Baseline cardiologist's interpretation.

Electrocardiogram variable values will be considered PCI if they meet the criteria listed in Table 7. The number and percentage of subjects with post-baseline PCI values will be presented at each post-Baseline visit and for overall post-Baseline. For the by-visit summary, the numerator for the percentage is the number of subjects with a post-Baseline PCI ECG for the given parameter and visit, and the denominator is the number of subjects with non-missing values for the given parameter and visit. For the overall post-Baseline summary, the numerator for the percentage is the number of subjects with at least 1 post-Baseline PCI ECG for the given parameter, and the denominator is the number of subjects with at least 1 post-Baseline ECG value for the given parameter. A listing of all subjects with any PCI ECG values will be provided.

Table 7 Criteria for Potentially Clinically Important ECG Values

ECG Parameter	Unit	High PCI Criteria
QRS Interval	msec	≥120
PR Interval	msec	≥220
QTcB	msec	>500
QTcF	msec	>500
QTcB: change from baseline		>60 msec
QTcF: change from baseline		>60 msec

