15.6 Physical Examination

Physical examinations are performed throughout the study at every visit in the clinic. When a study visit takes place off-site, the physical examination is not required. Physical examination results (normal, abnormal, and not done) will be summarized in a frequency table by body system and analysis visit. A listing of abnormal physical examination data will be provided.

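### SAP 15.6 tabulates physical examination results as marginal counts, with no link to each girl's Baseline and no stated denominator

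*Protocol*

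**What the plan says.** **Schedule.** Protocol 6.3.1 states: "A general physical examination will be conducted at Screening, Baseline, and Visits 3, 4, 5, 6, 7, 8, 9, and 10". The examination covers eight organ systems, of which the genitourinary is optional. The same section adds: "When a study visit takes place off-site, the physical examination will not be required".

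**Which visits can be off-site.** Protocol 3.1.2 and footnote c of Table S-1 say: "The Baseline and Week 12 visits must be done at the clinic". For the end of treatment, footnote a of Table S-2 says: "The EOT visit should be done in the clinic whenever possible". The note at the start of the synopsis defines *should* as a recommendation, not a requirement. Seven of the eight post-Baseline visits can therefore take place without an examination.

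**Analysis.** SAP 15.6 says: "Physical examination results (normal, abnormal, and not done) will be summarized in a frequency table by body system and analysis visit", and "A listing of abnormal physical examination data will be provided". It gives no shift from Baseline, no worst post-Baseline result and no denominator. The general rule in SAP 5.1 calls for counts and percentages per category and does not define the denominator for this table either.

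**Comparators in the same SAP.** SAP 15.3 plans laboratory shift tables with paired denominators. SAP 15.5 deals with the cardiologist's normal/abnormal ECG reading and says that the "interpretations will also be summarized in a shift table". It gives paired denominators and a shift to the worst post-Baseline reading.

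**Endpoint.** Protocol 2.1.1 and SAP 15.1 include among the four safety endpoints "potentially clinically important changes in other safety assessments".

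**The concern.** A physical examination result by body system has the same structure as the ECG interpretation: normal or abnormal, recorded at Baseline and repeatedly afterwards. The SAP pairs one with Baseline and leaves the other as separate counts per visit. Two weaknesses follow.

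1. Separate counts give only the net change. A girl whose finding resolves cancels a girl with a new one, so a body system can look unchanged when it is not. This applies at every visit, Week 12 included.
2. Not-done is listed as a category beside normal and abnormal, and the denominator is unstated. If percentages are taken over all girls, the abnormal percentage falls whenever girls are seen off-site and not examined, with no clinical change.

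At stake is how well one descriptive safety table in a study of 10 to 15 girls can be read. No test or decision rule depends on it.

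**Working it through.** The documents give no figure on this point: no expected abnormality rate and no expected share of off-site visits. There is nothing to reproduce. The sample sizes 10 and 15 come from Protocol 9.3; every other count below is an assumption chosen to show the range.

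**Check 1: what two marginal counts say about new abnormalities.** Let N girls be examined at both visits, with *a* abnormal at Baseline and *b* abnormal at the later visit. The number with a new abnormality lies between max(0, *b* − *a*) and min(*b*, N − *a*).

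| N | *a* | *b* | Minimum new | Maximum new |
|---|---|---|---|---|
| 15 | 9 | 9 | max(0, 0) = 0 | min(9, 6) = 6 |
| 10 | 6 | 6 | max(0, 0) = 0 | min(6, 4) = 4 |
| 15 | 6 | 8 | max(0, 2) = 2 | min(8, 9) = 8 |
| 15 | 0 | 2 | max(0, 2) = 2 | min(2, 15) = 2 |
| 10 | 10 | 10 | max(0, 0) = 0 | min(10, 0) = 0 |

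The table is uninformative about new findings mainly when a body system has a middling Baseline rate. It is exact when nobody is abnormal at Baseline, or when everybody is. A shift table replaces each range with a count.

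**Check 2: effect of the denominator.** Let *p* be the true abnormal share and *k* the number not examined, with examination unrelated to findings. The expected abnormal percentage is *p*(N − *k*)/N if not-done girls are in the denominator, and *p* if only examined girls are counted.

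With N = 15 and *p* = 9/15 = 60%:

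| *k* not examined | Not-done in denominator | Examined only |
|---|---|---|
| 0 | 0.60 × 15/15 = 60% | 60% |
| 3 | 0.60 × 12/15 = 48% | 60% |
| 6 | 0.60 × 9/15 = 36% | 60% |
| 9 | 0.60 × 6/15 = 24% | 60% |

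With 40% of girls unexamined (6 of 15 or 4 of 10), true rates of 20%, 40%, 60% and 80% would read 12%, 24%, 36% and 48%. Off-site visits cannot cause such a fall at Baseline or Week 12.

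**The case against.** The strongest reply is that the information reaches the reader anyway, and most of that reply stands.

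- A reader might infer that the planned table cannot show a new abnormality. The documents do not support that. Baseline is an analysis visit (SAP 5.6), the table is by body system, and any rise in the count proves a minimum number of new findings.
- A reader might also infer that the abnormal rate *will* fall as visits move off-site. That needs two things the SAP does not say: that not-done girls are in the denominator, and that an unperformed off-site examination is entered as not done. If it is, the printed not-done count lets a reader recompute the rate among examined girls.
- Off-site examinations are not required, which is weaker than omitted. Off-site visits need prior approval from the Sponsor or Medical Monitor.
- There are other routes for a new finding. SAP 5 lists all data. Under Protocol 7.1.1 an unfavorable sign can be an adverse event, while stable conditions present before Baseline are not. SAP 15.2 tabulates treatment-emergent events by organ class and term.
- Protocol 9.5.2 plans change from Baseline for ECG, vital signs, weight and laboratory values, not for the examination. SAP Tables 4 to 7 hold no examination criterion. SAP 15.6 therefore does not fall short of the protocol.

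What the reply does not reach is the table itself. Pairing by hand from listings is possible with 10 to 15 girls, but the listing specified in SAP 15.6 holds abnormal results only, so a missing Baseline entry there could mean normal or not examined. Recording a sign as an adverse event depends on the investigator's judgement and leaves the table as it is.

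**Conclusion.** The point holds in a limited form. SAP 15.6 gives marginal counts without a Baseline link and without a denominator, whereas SAP 15.3 and 15.5 supply both for laboratory values and ECG readings. Offsetting changes within a body system are hidden; in the illustrative case of 9 of 15 abnormal at both visits, 0 to 6 girls could have a new abnormality. The fall in the abnormal percentage is conditional on the unstated denominator and on unperformed examinations being recorded as not done.

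The documents do not support calling this a failure to analyse a primary endpoint or a loss of safety signals: adverse events and full listings remain, and every analysis is descriptive. It is a free improvement that applies a method the SAP already uses to data already collected.

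**What to change.** In SAP 15.6:

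1. Add a shift table by body system from Baseline (normal, abnormal) to each visit and to the worst post-Baseline result. Follow SAP 15.5 for denominators: girls examined at Baseline and at that visit for the by-visit shift, and girls examined at Baseline and at least once afterwards for the worst result.
2. Report not-done as a count outside the percentages.
3. Flag normal-to-abnormal changes in the listing.

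The cost is SAP wording, one table shell and a listing flag. No visit, procedure or data field changes.

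One limit should be acknowledged. A normal/abnormal shift does not show worsening in a system already abnormal at Baseline. That is likely for the neurological system in most girls, because classic Rett syndrome requires gait abnormality and hand stereotypies (Protocol Appendix A). Girls under 3 with possible Rett syndrome may differ.

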6.3.2 Vital Signs

Vital signs will include body temperature, resting respiration rate, sitting systolic and diastolic blood pressure, and pulse rate. The sitting blood pressure will be measured after the subject has been sitting or supine for ≥ 3 minutes.

Vital signs to be measured at Screening, Baseline, Visits 3, 4, 5, 6, 7, 8, 9, and 10.

6.3.3 Height, Weight, and Body Mass Index

Height will be measured at Screening and at Visits 6 and 10.

Weight will be measured at Screening, Baseline, and Visits 3, 4, 5, 6, 7, 8, 9, and 10 when the visit takes place in the clinic. When a study visit takes place off-site, weight should be measured whenever possible.

Body mass index will be calculated using the following formula: Weight (kg) / [height (m)] 2 .

6.3.4 Electrocardiograms

All ECGs will be complete, standardized recordings appropriate for the age of the subject, whenever possible. ECGs will be completed in triplicate at Visit 1 (Screening), at Visit 2 (Baseline) predose and at 2 hours (±15 minutes) after dosing, and at Visit 6 (Week 12). A single ECG will be completed at Visit 3 (Week 2), and Visit 4 (Week 4), Visit 5 (Week 8),

Study: ACP-2566-009 Clinical Study Protocol Amendment 2

Visit 7 (Week 24), Visit 8 (Week 52), Visit 9 (Week 78), and Visit 10 (Week 104). For visits at which more than one ECG is completed, the average QTcF interval of all legible ECGs will be used to determine the QTcF interval for that visit.

The subject should rest for ≥5 minutes in a supine position before the ECG is obtained. If it is impractical to rest in supine position due to the subject's medical condition, the subject may remain in a partial supine or other position (e.g., upright in wheelchair) for ≥5 minutes before the ECG is obtained and when the ECG is obtained. ECG tracings (paper or electronic) will be reviewed and interpreted by a qualified clinician for prolongation of the QTcF interval and for other cardiac irregularities. ECG tracings and results (ventricular rate, PR interval of ECG, QRS interval of ECG, QT, QTcF, and QTcB intervals) will be included in the subject's study records.

ECGs will also be read by a qualified central reader. The central reading will be the reading that is entered in the database. The results from the reports from the central reader will also be reviewed by the Investigator. At Screening and Baseline, the average QTcF interval of all legible ECGs will be used to determine eligibility.

If the average QTcF value from the set of ECGs done at Screening is prolonged due to an identifiable cause, and it is medically appropriate to address that cause, a repeat set of triplicate ECGs may be performed during the Screening period and before the Baseline visit with the agreement of the Medical Monitor. In this case, the repeat ECGs will be used in determination of subject eligibility.

6.3.4.1 Post-Baseline QTcF Interval Stopping Criteria

In the event that a post-Baseline QTcF duration of ≥500 ms or an increase of ≥60 ms compared to the average QTcF interval at Baseline (before dosing) is observed, study drug administration is to be discontinued. For visits at which more than one ECG is completed, the average QTcF interval of all legible ECGs will be used to determine the QTcF interval for that visit.

6.3.5 Laboratory Evaluations

Laboratory evaluations will be completed according to the schedule presented in Table S–1 and Table S–2, and procedures detailed in the laboratory manual. Additional safety testing may be performed at the discretion of the Investigator or designee. Laboratory testing may be repeated during the Screening period with agreement of the Medical Monitor if the Investigator suspects that a laboratory abnormality is a temporary or reversible finding.

Clinical laboratory sample collection is not required to be completed under fasting conditions. The laboratory evaluations will include the following:

Final Version: 1.0

- Clinical chemistry serum tests
 - Sodium (Na), potassium (K), chloride (Cl), phosphorus (P), calcium (Ca),
 magnesium (Mg), carbon dioxide (CO₂), blood urea nitrogen (BUN), creatinine (CR), uric acid
 - Mg will only be performed at Visit 1 (Screening)
 - Alanine aminotransferase (ALT), aspartate aminotransferase (AST), gamma-glutamyl transpeptidase (GGT), alkaline phosphatase (ALP), total bilirubin (TBIL), lactate dehydrogenase (LDH)
 - Glucose
 - Albumin (ALB), total protein
 - o Thyroid stimulating hormone (TSH), free T3, and free T4
 - Thyroid function tests will be performed at Visit 1 (Screening)
- Hematology tests
 - o Complete blood count (CBC) including:
 - White blood cell (WBC) count
 - Complete differential (relative and absolute)
 - Hematocrit (Hct), hemoglobin, red blood cells (RBC), platelets
 - Reticulocyte count
- Urinalysis
 - o Blood, RBCs, WBCs, protein, glucose, ketones, specific gravity, pH
 - Reasonable efforts will be made to collect a urine sample from all subjects. When collection of a urine sample proves impractical or impossible (e.g., because the subject is incontinent or unable to cooperate), failure to collect a urine sample will be recorded in the subject's eCRF, and will not be considered a protocol deviation.

6.4 Caregiver Diary

A semi-structured caregiver diary will be completed during screening and treatment in which caregivers will record seizures and seizure-like spells if they are present.

At the Screening visit, the clinician will review the subject's seizure profile (if applicable) and will help the family to characterize the subject's typical seizure types. These are recorded in the caregiver diary.

Study drug dosing and concomitant medication dosing will be recorded in the caregiver diary. Instances of missed or partial doses that occur on any day of the study will also be recorded

The caregiver diary will be completed and collected on an ongoing basis throughout the study beginning at Screening. The clinician will verbally ask about AEs (see Section 7.4.1), review the events recorded in the diary with the caregiver and will make a clinical evaluation, including an evaluation of whether an adverse event will be reported.

